10.4 Off study criteria

- Completion of the 12-month follow-up
- The subject voluntarily withdraws
- Significant subject non-compliance with follow-up visits
- Death

11.0 ADVERSE EVENT REPORTING

11.1 Definitions

Adverse events: Any untoward medical occurrence in a human subject, including any abnormal sign (e.g., abnormal physical exam or laboratory finding), symptom, or disease, temporally associated with the subject's participation in the research, whether or not considered related to the subject's participation in the research.

This will include:

- Expected events related to the subject's disease process during active enrollment in the research protocol and do not directly result from use of the investigational device or study.
- Procedural events directly related to the cardiac catheterization procedure and recovery from the procedure and do not directly result from use of the investigational device.

Serious Adverse Event (SAE): A serious adverse event that results in any of the following and NOT directly related to the device. This includes any event that

- Results in death
- Is life-threatening (places the subject at immediate risk of death from the event as it occurs);
- results in in-patient hospitalization or prolongation of existing hospitalization;
- results in a persistent or significant incapacity;
- results in a congenital anomaly/birth defect (not relevant to this study); or
- based upon appropriate medical judgment, may jeopardize the subject's health and may require medical or surgical intervention to prevent one of the other outcomes listed in this definition.

Adverse Device Effect (ADE): Any untoward or unintended response to a medical device. This definition includes any event resulting from insufficiencies or inadequacies in the instructions for use or the deployment of the device or any event that is a result of user error.

During this clinical investigation, an event should be considered related to the device when it is the result of:

- BASILICA procedure
- Asahi-Intecc Astate XS 20 guidewire

An event will be considered NOT related to the BASILICA procedure when it is the result of:

- A pre-existing medical condition
- Clearly attributable to TAVR but not BASILICA part of procedure (example: apical left ventricular perforation)

Anticipated Adverse Device Effects (ADEs): An ADE is an adverse event with a reasonable possibility that the device or procedure caused or contributed to the event. The following ADEs are considered anticipated based on previous human experience:

- BASILICA device procedure failure including failure to traverse, to lacerate, or to position catheters or guidewires
- BASILICA device mechanical failure including wire fracture, including causing embolization requiring retrieval

- Embolization of air, valve debris, atheroma, or thrombus to coronaries, brain, limbs, or viscera causing myocardial infarction, stroke, or limb ischemia
- Mitral valve injury such as chordal disruption causing deterioration in mitral valve function
- Hemodynamic instability during BASILICA caused by traction on the aortic valve leaflets, or after BASILICA caused by acute or acute-on-chronic aortic valve regurgitation
- Electrical coupling of traversal or laceration system and other conductive structures such as THV guidewire
- Other mechanical device failure
- Allergic reaction to anesthesia, contrast media, or device materials
- Valve malposition, reposition, dislocation, migration, or embolization or deployment in unintended location
- Prosthetic valve dysfunction, including stenosis, regurgitation and patient-prosthesis mismatch, causing symptoms or requiring unplanned re-intervention
- Transcaval shunt, for example, from aorta to left atrium
- Coronary artery injury
- Atrial-ventricular conduction defects to include bundle branch block and complete heart block requiring placement of a temporary or permanent pacemaker
- Cardiac arrhythmia including ventricular fibrillation
- Transient myocardial dysfunction attributed to rapid ventricular pacing required for aortic valve implantation, including bradycardia or pulseless electrical activity, or requiring cardiopulmonary resuscitation
- Angina and myocardial ischemia or myocardial infarction
- Coronary artery obstruction or injury that may require intervention, which may represent a failure of BASILICA
- Congestive heart failure, elevated natriuretic peptides, or cardiogenic shock that may require intervention
- Infective endocarditis or other infective complications of TAVR
- Infection or sepsis including access sites, lung, urinary tract, or other system infection related to procedure or its complications
- Left ventricular, ventricular septal, or left atrial perforation or pseudoaneurysm
- Pericardial effusion or tamponade
- Hypertension
- Hypotension requiring fluid resuscitation, vasopressor support or mechanical circulatory support or chest compressions
- Stroke, transient ischemic attacks, or seizure
- Hemolysis (defined as anemia requiring transfusion with significant or dramatic schizocytes on peripheral blood examination and depressed haptoglobin)
- Low platelets or thrombocytopenia
- Mechanical injury to the myocardium, access vasculature, cardiac valves that may require intervention
- Bleeding leading to anemia and blood transfusions
- Aortic valve thrombosis
- Retroperitoneal bleed, hematoma, fistula, or other access site injury
- Contrast-induced nephropathy requiring temporary or permanent hemodialysis or medical treatment
- Volume overload, pleural effusion, or dyspnea from procedure-related volume perturbations
- Respiratory insufficiency failure requiring oxygen therapy, mechanical support or mechanical ventilation

- Pain including back pain, access site pain, and generalized pain
- Mechanical circulatory support including emergency cardiopulmonary bypass
- Emergency cardiac surgery
- Cardiac arrest
- Death

Serious Adverse Device Effect (SADE): An adverse effect that may have been or is attributed to the use of the device and produce an injury or illness that is life-threatening, results in permanent impairment or damage to the body, or requires medical or surgical intervention to prevent permanent harm to the body.

Unanticipated Adverse Device Effect (UADE): Any serious adverse effect on health or safety or any life-threatening problem or death caused by, or associated with, a device, if that effect, problem, or death was not previously identified in nature, severity, or degree of incidence in the investigational plan or application (including a supplementary plan or application), or any other unanticipated serious problem associated with a device that relates to the rights, safety, or welfare of subjects (21 CFR 812.3(s)).

Unanticipated Problem (UP): An unanticipated problem is any incident, experience, or outcome that meets ALL of the following criteria:

- Unexpected in terms of nature, severity, or frequency in relation to:
 - a. the research risks that are described in the IRB-approved research protocol and informed consent document, Investigator's Brochure or other study documents, and
 - b. the characteristics of the subject population being studied, and
- Related or possibly related to participation in the research, and
- Places subjects or others at a greater risk of harm (including physical, psychological, economic, or social harm) than was previously known or recognized.

Protocol Deviation: A protocol deviation is any change, divergence, or departure from the study design or procedures of an IRB-approved research protocol.

Non-Compliance

Non-compliance is defined as failure to comply with applicable NIH Human Research Protections Program (HRPP) policies, IRB requirements, or regulatory requirements for the protection of human research subjects.

Non-compliance may be further characterized as:

1. Serious non-compliance: Non-compliance that:
 - a. Increases risks, or causes harm, to participants.
 - b. Decreases potential benefits to participants.
 - c. Compromises the integrity of the NIH HRPP.
 - d. Invalidates the study data.
2. Continuing non-compliance: Non-compliance that is recurring.
3. Minor (non-serious) non-compliance: Non-compliance that is neither serious nor continuing.

11.2 Adverse event management:

The following adverse event management guidelines are intended to ensure the safety of each subject while on the study. Adverse events and adverse device effects will be attributed to study procedure and graded by severity according to the following tables:

11.2.1 Grading of adverse events and adverse device effects

Category	Description
Mild	Awareness of symptom. Not expected to have a clinically significant effect on the subject's condition. Not surpassing the expected standard medical intervention.
Moderate	Condition creates a level of discomfort that interferes with the subject's usual activity or affects clinical status. May require medical intervention.
Severe	Incapacitating and significantly affects the subject's clinical status. Likely requires medical intervention and prolonged hospitalization.

11.2.2 Attribution of adverse events to the research protocol

The relatedness of adverse events will be classified as:

Classification	Description
Definite	The event is clearly related to the research protocol.
Probable	The event is likely related to the research protocol. The event has a reasonable temporal relationship to the research device or research procedure and alternative causes, such as underlying disease, concomitant medications, or concomitant treatment-can be excluded.
Possible	The event may be related to the research protocol. The event has a reasonable temporal relationship to the research device or research procedure, and attribution of the event to the device or procedure cannot be excluded. However, alternative causes—such as underlying disease, concomitant medications, or concomitant treatments—are presumably responsible.
Unlikely	It is doubtful the event is related to the research protocol. The event can reasonably be explained by other factors, including underlying disease, concomitant medications, or concomitant treatments.
Unrelated	The event is clearly not related to the research protocol. There either is no temporal association with the research device or procedure, or the event is readily explained by other factors, including underlying disease, concomitant medications, or concomitant treatments.

11.2.3 Adverse Event Reporting

Adverse event recording will start on Day (0) of the BASILICA TAVR procedure and will continue through the 12 month Follow Up. New events or conditions present at baseline that increase in severity will be recorded and evaluated and reported on the case report form. Once the subject has completed the 30 day follow up, only serious adverse events (SAE), serious adverse device effects (SADE), unanticipated device effects (UADE) and unanticipated problems (UP) will be reported to the Sponsor. It is the responsibility of the site investigator to report adverse events and adverse device effects to their respective IRBs or other regulatory bodies according to their reporting requirements. Monitoring visits will be conducted by the Sponsor to review source documentation, and accuracy and completion of the adverse event case report forms.

11.2.4 Adverse event reporting timeframes:

Serious Adverse Events (SAEs)

- All serious adverse events will be reported to the Sponsor immediately but not later than 3 working days from the event. The respective institutional IRB should be notified according to their requirements.
- The serious adverse event will be evaluated by the sponsor. If determined to be an unanticipated adverse device effect that increases the risk to the participating subjects, the sponsor will terminate the investigation within 5 days after making the determination, and not later than 15 working days after the sponsor was first notified of the event. [21 CFR 812.46]

Unanticipated Adverse Device Effects (UADE)

- Must be reported to the Sponsor and the institutional IRB immediately but no later than 10 working days after the investigator learns of the event. [21 CFR 812.150]
- Unanticipated Adverse Device Effects should be reported via telephone as well as on the adverse event section of the case report form.
- If the event is determined by the Sponsor to be a UADE, the Sponsor will report the event to all investigators to enable reporting to their respective IRB/regulatory bodies. The Sponsor will provide this notification to participating sites and to the FDA within 10 working days after they first receive notice of the effect. [21 CFR 812.150]
- All Unanticipated Adverse Device Effects will be reported by the Sponsor to the NHLBI IRB immediately upon notification but no later than 10 working days.

Deaths

- The investigator will notify the Sponsor immediately but within 3 working days of notification of a subject's death, whether the death is device related or clinical condition. Institutional IRB's will be notified according to the specific institutional regulatory requirements for reporting a death.
- The Sponsor will notify the NHLBI IRB of a subject's death within 7 days.
- A subject's death will be recorded on the Case Report Form.

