Hemodynamics are recorded quickly after laceration before TAVR. Coronary artery stent systems are positioned prophylactically at the discretion of the operator. Predilatation, including intentional disruption of the bioprosthetic valve frame, is performed at operator discretion, before or after TAVR. Then TAVR is performed using established techniques typically during rapid ventricular pacing. The device size and inflation volumes are selected and applied at the discretion of the operator. Post-dilatation is performed at operator discretion to achieve an optimum TAVR result. Coronary artery patency is established using angiography and, if employed, using prepositioned pressure-tip guidewires. Coronary artery pressure (instantaneous wave-free ratio, *iFR*) may further be examined if possible at the discretion of the operator.

Completion hemodynamics and echocardiography are recorded. Finally, percutaneous femoral artery and vein vascular hemostasis is obtained and the subject convalesces in the appropriate inpatient recovery unit.

Before discharge, follow-up transthoracic echocardiography is recorded. A single contrast-enhanced CT of the heart is obtained before discharge if renal function allows, otherwise it is deferred as long as 30-days. Blood tests are recorded for research only as obtained for medical care.

Anticoagulation and antiplatelet therapy is prescribed after discharge at the physicians' discretion, and is recorded.

All subjects are to be enrolled in the TVT-Registry postmarketing TAVR registry.

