30-day (± 14 days)	
Clinic/office visit to update subject's vital status to include:
 
 • Vital signs • ECG • Medication Assessment • NYHA Classification • Surface Echocardiogram and/or transesophageal • Cardiac CT scan contrast enhanced, gated dynamic if not conducted pre-discharge for clinical reasons • Clinical blood work is captured for research including: 
 CBC with platelets Haptoglobin Chemistry Panel PT INR BNP/Pro-BNP • TVTRegistry quality surveillance data, including QOL • Adverse Event Assessment
12 month (± 30 days)	
Clinic/office visit to update subject's vital status to include:
 
 • Vital signs • Medication Assessment • NYHA Classification • Surface Echocardiogram and/or transesophageal • Clinical blood work is captured for research including: 
 CBC with platelets Haptoglobin Chemistry Panel PT INR BNP/Pro-BNP • TVTRegistry quality surveillance data, including QOL • Adverse Event Assessment

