10.2.2 Primary safety endpoint

The primary safety endpoint is freedom from major adverse clinical events (MACE) according to VARC-2 at 30days.

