10.2.3 Secondary Endpoints

Secondary endpoints include

- Technical success, defined as clinical success irrespective of coronary artery stenting
- Clinical success without stroke, as determined by site physicians
- Technical success of BASILICA only (delivery and removal of BASILICA catheter equipment, traversal, and laceration of intended aortic leaflet)
- Coronary artery obstruction measured as instantaneous wave-free pressure ratio (iFR) or related measurements using a solid-state pressure-transducer guidewire, if measured
- Survival to discharge, to 30d, and to 12mo
- Neurological events as reported by the site clinicians
- Access and vascular complications
- Peri-procedural and spontaneous acute myocardial infarction
- Pericardial effusion or tamponade
- VARC-2 bleeding complications
- AKIN acute kidney injury
- Freedom from hemolytic anemia related to BASILICA TAVR
- BASILICA Device or Procedure related technical failure: acute embolism, mitral valve injury, traversal into left atrium, coronary artery injury induced by BASILICA, etc.
- Rotational orientation of transcatheter heart valve commissures with regard to coronary artery ostia

- Hemodynamic instability caused by BASILICA before TAVR
- TAVR thrombosis on CT or echocardiography during follow-up
- Endocarditis during follow-up
- Outcomes for laceration of native versus surgical aortic valves, for single versus double scallop laceration, and for procedures with versus without bioprostheses intentional overexpansion

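### An early 30-day visit leaves Day-30 status to passive reporting, and going off study for visit non-compliance leaves 12-month vital status unfollowed

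*Combined protocol and SAP*

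**What the plan says.** **Endpoints.** The primary safety endpoint in Section 10.2.2 is "freedom from major adverse clinical events (MACE) according to VARC-2 at 30days". Section 10.2.3 lists "Survival to discharge, to 30d, and to 12mo" among the secondary endpoints, along with bleeding, vascular complications and acute kidney injury. Section 10.2 plans Kaplan-Meier estimates of overall and event-free survival. Sections 10.3.2 and 10.3.3 base stopping on counts of deaths within 30 days. Section 6.7 expects the main manuscript to rest on 30-day data.

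**Visits.** Sections 6.5 and 6.6 give the 30-day visit a window of ±14 days. The next visit is at month 12, with a window of 4 weeks in Section 6.5 but "12 month (± 30 days") in Section 6.6.

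**Event reporting.** Section 11.2.3 states: "Adverse event recording will start on Day (0) of the BASILICA TAVR procedure and will continue through the 12 month Follow Up". It then narrows what goes to the sponsor: "Once the subject has completed the 30 day follow up, only serious adverse events (SAE), serious adverse device effects (SADE), unanticipated device effects (UADE"), plus unanticipated problems. Section 11.2.4 adds: "All serious adverse events will be reported to the Sponsor immediately but not later than 3 working days from the event". It also requires the investigator to notify any death within 3 working days of being informed of it, whatever the cause.

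**Leaving the study.** Section 10.4 lists "Significant subject non-compliance with follow-up visits" as an off-study criterion, separate from voluntary withdrawal. How much non-compliance counts as significant is not defined.

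**Registry.** Section 6.4 states: "All subjects are to be enrolled in the TVT-Registry postmarketing TAVR registry". The registry items that Section 6.5 lists for capture are KCCQ-12 and baseline frailty.

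**The concern.** The 30-day safety result should describe what happened to each subject through Day 30. Here the switch to narrower reporting is tied to a visit that can fall two weeks before that day, and nothing scheduled afterwards confirms the subject's status at Day 30 before the 30-day results are written up. Section 6.5 returns subjects to their own physicians for continuing care, so the site may not hear promptly of an event treated elsewhere. The duty to report a death runs from when the site learns of it.

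The off-study rule raises a related problem for the 12-month endpoint. Section 14.3, justifying a consent waiver for earlier BASILICA patients, describes them as very sick and old, often with poor survival and severe disability. In such a population missed visits may reflect decline. Ending follow-up for that reason would make censoring depend on prognosis, which Kaplan-Meier estimation assumes it does not.

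Both rules can err only in the favourable direction for safety and survival.

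**Working it through.** **1. The visit window.** Input: 30 ± 14 days (Sections 6.5 and 6.6).

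- Earliest visit: 30 − 14 = Day 16. Latest: 30 + 14 = Day 44.
- Days of the 30-day period after the earliest visit: 30 − 16 = 14, or 14/30 = 47%.
- A visit on or after Day 30 leaves no gap.

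**2. What changes once the visit is complete.**

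| Item | Before the visit | After the visit |
|---|---|---|
| Recording at the site | Yes | Yes, to month 12 |
| Serious events, serious or unanticipated device effects, unanticipated problems: to sponsor | Yes | Yes |
| Deaths: to sponsor | Yes | Yes |
| Non-serious events: to sponsor | Yes | No |
| Next scheduled contact | 30-day visit | Month 12 |

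Two things are lost after an early visit: active checking, and non-serious events reaching the sponsor.

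**3. The plan's own figures that need complete 30-day death counts.** The boundary is the smallest k with P(p > p0 | Beta(a + k, b + n − k)) ≥ 0.90. With a = 0.9, b = 5.1, p0 = 0.15, and with a = 1.2, b = 4.8, p0 = 0.20, both printed boundaries are reproduced for every n up to 30. An exact binomial recursion, applying the boundary after each subject, gives for the stratum without overexpansion:

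| True 30-day mortality | 10% | 15% | 20% | 25% | 30% | 35% |
|---|---|---|---|---|---|---|
| Stopped, Section 10.3.2 | 4.8% | 17.3% | 39% | 62.3% | 81.3% | 92.2% |
| Stopped, exact | 4.8% | 17.5% | 38.9% | 62.4% | 81.0% | 92.2% |

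The figures are sound. They assume that every 30-day death is counted. If 5, 10 or 20% of deaths went uncounted (an assumption), the stopping probability would fall from 62.4% to 56.7, 50.9 or 38.9% at 25% mortality, and from 81.0% to 76.2, 70.7 or 57.9% at 30%. This shows sensitivity only. The reporting rule does not exempt any death.

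**4. Survival at 12 months.** Each death among 30 subjects is 1/30 = 3.3 points. For a bound, assume one death before Day 30, m subjects taken off study and censored just after Day 30, and D observed deaths in all. None of these values is in the documents.

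- Kaplan-Meier: S = (29/30) × (1 − (D − 1)/(29 − m)).
- Worst case, every off-study subject died: (30 − D − m)/30.

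For D = 3:

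| m | Kaplan-Meier | Worst case | Gap (points) |
|---|---|---|---|
| 1 | (29/30)(1 − 2/28) = 89.8% | 26/30 = 86.7% | 3.1 |
| 2 | (29/30)(1 − 2/27) = 89.5% | 25/30 = 83.3% | 6.2 |
| 3 | (29/30)(1 − 2/26) = 89.2% | 24/30 = 80.0% | 9.2 |

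For D = 5 the gaps are 2.9, 5.7 and 8.5 points. These are outer limits, not estimates.

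**The case against.** The case against is substantial.

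- **Observation is not ended by rule.** A reader might infer that event reporting stops at a Day-16 visit. It does not: sites keep recording to month 12, and serious events and deaths must still be reported. The definition of a serious event covers death, life-threatening events and hospitalization, so most major events should fall under it. This stands.
- **Other checks exist.** Adverse events are assessed again at month 12, monitors compare forms with source documents (Section 15.3), and the events committee reviews deaths, primary endpoints and site-reported strokes in the first year (Section 10.2.5). These help, but they depend largely on what the site knows or has on file, and the month-12 assessment may come after the 30-day manuscript.
- **The effect on MACE cannot be sized.** A reader might infer that a true rate of 20% would appear as 14 to 18% if 10 to 30% of events fell after Day 16. That needs every subject to be seen on Day 16 and every later event to be missed. The duty to report serious events contradicts this, and the components of MACE are not listed. The range should not be used.
- **The off-study rule is narrower than any missed visit.** It requires significant non-compliance, and Section 8.0 expects high retention. The documents do not say that such subjects are censored; no censoring rule is given. Informative loss is therefore a risk, not a finding.
- **The study is small and descriptive.** An exact 95% interval for 6 of 30 runs from about 8 to 39%, wider than any likely bias. But that interval does not reflect missed events, and the remedy is cheap.

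A reader might also infer that the registry already supplies vital status. The capture listed in Section 6.5 does not show that.

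**Conclusion.** The point holds in two parts.

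For a subject seen before Day 30, status at Day 30 rests on passive reporting for up to 14 of 30 days, and non-serious bleeding, vascular or kidney events in that gap need not reach the sponsor. This affects the primary safety endpoint, 30-day survival and the inputs to the stopping rules through late or missed detection. The documents do not support saying that serious events or deaths cease to be reportable.

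The off-study rule can remove subjects who have not withdrawn consent, and no vital-status follow-up is provided for them. If that loss is related to deterioration and those subjects are censored, 12-month survival is overstated. The direction follows from these conditions. The size does not: the documents give no rate of early visits, of non-compliance or of events after an early visit. The only firm scale is about 3 points per uncounted death among 30 subjects.

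**What to change.** 1. In Section 11.2.3, continue full adverse-event reporting to Day 30 or the 30-day visit, whichever is later. In Sections 6.5 and 6.6, require a vital-status and event contact on or after Day 30 when the visit was earlier; a telephone call is enough.
2. In Section 10.4, do not let visit non-compliance end outcome follow-up. Keep these subjects in follow-up for vital status and events unless they withdraw consent, and add vital status to the registry or site data capture.
3. In Section 10.2, state the censoring rule and report 12-month survival with a worst-case sensitivity analysis that counts any subject still lost as a death.
4. In the same edit, reconcile the two 12-month windows in Sections 6.5 and 6.6.

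The cost is wording in these sections, at most one call per early-visit subject and a little tracing work. No added visit or test is needed.
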